## **Survey Instrument**

A structured, close-ended and self-reported questionnaire with a five-point Likert scale was used. The questionnaire was designed to measure HBM constructs (e.g. perceived susceptibility, severity, benefits, barriers, cues to action, and self-efficacy), awareness of oral health and oral hygiene related behaviors. A panel of four subject matter experts reviewed the instrument, including two dentists, a public health specialist and an endocrinologist. Each expert independently evaluated the questionnaire items by using a four-point relevance scale, ranging from "not relevant" to "highly relevant." Their ratings were used to calculate content validity indices, Items with poor expert agreement ( $I-CVI \leq 0.25$ ) were removed, while items with minor disagreement ( $I-CVI = 0.75$ ) were revised for clarity. Items with strong relevance ratings ( $I-CVI = 1.00$ ) were retained as it is in the final questionnaire. The  $S-CVI/Ave$  for the final instrument was 0.89, which indicates good content validity. The universal agreement index ( $S-CVI/UA$ ) was 0.83, indicating that 83% of the items received unanimous relevance ratings from all four experts.(15)

The final questionnaire consisted of three major sections, designed to assess oral-health knowledge, HBM constructs, and behaviors among individuals with Type 2 Diabetes. Section I comprised of 10 items assessing oral-health knowledge. Section II included the HBM constructs, which was subdivided into

seven domains: Perceived Susceptibility (7 items), Perceived Severity (10 items), Perceived Barriers (6 items), Perceived Benefits (6 items), Self-Efficacy (7 items), Internal Cues to Action (4 items) and External Cues to Action (5 items). Section III was focused on oral-hygiene behaviors, comprising 10 items which measured the frequency and consistency of participants' oral-health behaviors.

The Cronbach's alpha value of the final instrument was calculated after the pilot study in which 30 participants filled the questionnaire which was 0.783. (16)

## **Scoring**

The awareness questions section was scored such that each correct answer received 1 point, and each incorrect answer received 0 points. The total score for the awareness section was calculated based on maximum score of 10. The HBM constructs were assessed using five-point Likert scale, with response options ranging from "strongly agree" to "strongly disagree" and scored from 1 to 5, respectively. The scores for each model construct were calculated and reported within the range of 1 to 5. Similarly, the behavior questions were scored on a 5-point Likert scale of behavior evaluation, with responses ranging from "never" to "always" and scored from 0 to 4. In this study, higher scores indicate higher levels of awareness, perceived susceptibility, perceived severity, perceived benefits, perceived barriers, cues to action, self-efficacy, and performance of oral hygiene practices among diabetic patients.

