### **Perceived Susceptibility:**

How much diabetic patients think they might get oral health complications, measured using a Likert scale. (1 = Strongly Disagree to 5 = Strongly Agree). Higher scores reflect a greater perceived susceptibility. Pre and post intervention scores were compared, with cutoff levels based on the mean  $\pm$  SD. (7)

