### **Perceived Severity:**

Participants' perceptions of the severity of oral health complications and their potential impact on their overall wellbeing and diabetes management. Assessed through Likert scale statements rated from 1 (Strongly Disagree) to 5 (Strongly Agree). Higher scores indicate greater perceived severity. Pre and post scores will be compared using the mean and SD as cutoff criteria.(7)

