### **Perceived Benefits:**

Participants' beliefs about the positive outcomes of engaging in oral hygiene behaviors, such as prevention of oral complications. Assessed using Likert-scale items from 1 (Strongly Disagree) to 5 (Strongly Agree). Higher scores reflect

stronger perceived benefits. Pre and post intervention scores will be compared, and categorization will be done using the mean and SD. (7)

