**Perceived Barriers:**

Perception of participants about different challenges that hindered their ability to maintain proper oral hygiene. These self-reported barriers consist of financial constraints, time constraints, and insufficient knowledge or awareness about oral health care. Measured using items rated from 1 (Strongly Disagree) to 5 (Strongly Agree). Higher scores represent greater perceived barriers. Pre- and post-scores will be compared, with cutoffs based on mean  $\pm$  SD. (7)

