**Self-Efficacy:**

Confidence in performing and maintaining oral hygiene behaviors. It will be assessed via Likert scale items scored from 1 (Strongly Disagree) to 5 (Strongly Agree). Higher scores indicate greater self-efficacy. Pre- and post-intervention results will be compared, with cutoff scores determined by mean and SD. (7)

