**Cues to Action:**

Factors which include both Internal and external that motivate participants to involve in oral hygiene behaviors, such as family encouragement or healthcare provider advice. Assessed using a Likert scale. Higher scores denote stronger cues to action. Comparison of pre and post scores were done using the mean and SD for cutoff classification. (7)

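### The Scoring section numbers the Health Belief Model responses in the opposite direction to the construct definitions

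*Combined protocol and SAP*

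**What the plan says.** The Scoring section has one rule for all the HBM constructs: a five-point scale "ranging from 'strongly agree' to 'strongly disagree' and scored from 1 to 5, respectively". Construct scores are then reported on a 1 to 5 range. The section closes with a statement of direction: "In this study, higher scores indicate higher levels of awareness, perceived susceptibility", and it goes on to list the remaining HBM constructs and oral hygiene performance.

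The Operational Definitions give anchors construct by construct:

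- Perceived Susceptibility: "1 = Strongly Disagree to 5 = Strongly Agree). Higher scores reflect a greater perceived susceptibility"
- Perceived Severity: "rated from 1 (Strongly Disagree) to 5 (Strongly Agree). Higher scores indicate greater perceived severity"
- Perceived Benefits: "Assessed using Likert-scale items from 1 (Strongly Disagree) to 5 (Strongly Agree", with higher scores again meaning stronger perceived benefits
- Perceived Barriers: "Measured using items rated from 1 (Strongly Disagree) to 5 (Strongly Agree). Higher scores represent greater perceived barriers"
- Self-Efficacy: "scored from 1 (Strongly Disagree) to 5 (Strongly Agree). Higher scores indicate greater self-efficacy"
- Cues to Action, direction only: "Assessed using a Likert scale. Higher scores denote stronger cues to action"

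No section describes reverse-keyed items or a recoding step.

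**The concern.** The two parts of the document assign opposite numbers to the same answer. A participant who strongly agrees with a susceptibility item scores 1 under the Scoring section and 5 under the definition.

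What is at stake is the direction of the HBM results. Scored as the clause says, a rise in susceptibility or self-efficacy would be reported as a fall, and a fall in barriers as a rise. The definitions also set cutoffs from the mean and SD, and on a reversed scale the high and low categories would change places. These are not incidental variables: weeks 2 to 4 of the intervention are built around them, the Data Analysis Procedure tests them, and perceived susceptibility is the variable used for the sample size.

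**Working it through.** **1. The passages side by side**

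| Construct | Items (Survey Instrument) | Operational Definitions | Scoring clause | Conflict |
|---|---|---|---|---|
| Susceptibility | 7 | agree = 5 | agree = 1 | anchors |
| Severity | 10 | agree = 5 | agree = 1 | anchors |
| Barriers | 6 | agree = 5 | agree = 1 | anchors |
| Benefits | 6 | agree = 5 | agree = 1 | anchors |
| Self-efficacy | 7 | agree = 5 | agree = 1 | anchors |
| Cues, internal and external | 4 + 5 | higher = stronger, no anchors | agree = 1 | direction only |

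Explicit anchor conflict: 7 + 10 + 6 + 6 + 7 = 36 items. Direction-only conflict: 4 + 5 = 9 items. Together, 36 + 9 = 45, which is every HBM item.

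The word 'respectively' pairs the first label with the lowest number. The same section does this for behaviour, where never to always is scored 0 to 4, so the literal reading of the HBM clause is not strained. The section's last sentence then contradicts that clause, provided that agreeing with an item means more of the construct, as the five definitions imply.

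**2. Effect of a reversed 1 to 5 scale**

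Each score s becomes 6 − s. A mean m becomes 6 − m, the SD is unchanged, and any difference between groups or between time points changes sign.

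Inputs, from Sample Size (a previous trial's results, used only to illustrate): 4.09 (SD 0.49) for intervention, 3.64 (SD 1.01) for control, 49 per group.

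- As defined: 4.09 − 3.64 = +0.45.
- Reversed: 6 − 4.09 = 1.91; 6 − 3.64 = 2.36; 1.91 − 2.36 = −0.45.
- SE = √((0.49² + 1.01²)/49) = 0.160 under both codings.
- t = 0.45/0.160 = +2.81 as defined and −2.81 reversed. The two-sided p is 0.0061 (pooled) or 0.0065 (Welch) in both cases.

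The plan assigns the Mann-Whitney test to susceptibility. The same holds there: reversal turns U into n₁n₂ − U, with the same two-sided p. In the Wilcoxon signed rank test the positive and negative rank sums change places.

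**3. Sample size**

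The only stated design figure that uses an HBM score is 49 per group. With n = 2·SD²·(z for α/2 + z for power)²/δ², SD = √((0.49² + 1.01²)/2) = 0.794 and δ = ±0.45:

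- two-sided α 0.05 and 80% power give 49;
- two-sided α 0.01 and 95% power, as stated, give 111.

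Because δ is squared, both results are the same under either coding. That 49 does not follow from the stated α and power is a separate matter and has no bearing here.

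**The case against.** The strongest reply is that the intended direction is plain. Five definitions give identical anchors, the cues definition agrees in direction, and the Scoring section itself ends by saying that higher means more. One clause is the outlier, and the likeliest explanation is that two labels were written in the wrong order. Harm to the results would require the data to have been entered as that clause says, with no recode before analysis, and the document shows neither. A complete reversal might also be noticed in the descriptive statistics, since a group that improved would show beliefs falling and barriers rising.

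Much of this stands. The textual conflict is certain; an effect on the results is not. The hypothesis concerns knowledge and behaviour, whose scoring is not touched. Negatively worded items could in theory reconcile the texts, but none are described and the questionnaire is not in the document.

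What does not stand is treating the clause as harmless. It is in the section an analyst would follow when coding the data. Descriptive statistics are a weak safeguard: they expose a reversal only if the true change is large and its direction is already presumed, and barriers should move the opposite way from the other constructs.

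**Conclusion.** The concern holds. The scoring clause contradicts the explicit anchors of five constructs (36 items), the stated direction for cues to action (9 items) and the last sentence of its own section. Followed as written, it reverses the sign of every HBM construct result while leaving the size of each difference, the SDs, the two-sided p-values and the sample size as they were.

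The sign reversal assumes that agreement means more of the construct and that no recode was applied. Whether it occurred in this trial cannot be determined from the document. It should be settled before any HBM result is reported; the main hypothesis is not threatened.

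**What to change.** 1. Check the SPSS value labels against the questionnaire for all 45 HBM items, and note any negatively worded item in the same pass. Recode as 6 − s wherever strongly agree was entered as 1.
2. Reword the Scoring clause so that responses run from strongly disagree to strongly agree, scored 1 to 5 in that order.
3. Add the same anchors to the Cues to Action definition.
4. As a minor point of wording, align the Awareness definition (yes = 1, no = 0) with the Scoring rule (correct = 1, incorrect = 0). The two differ only if the correct answer to some item is no, which the document does not show.

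The cost is one check of the data file, a recode only if needed, and edits to one clause and two definitions.

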## **Intervention**

The intervention consisted of a four-week WhatsApp-based oral health education program based on HBM. The WhatsApp based intervention consisted of 12 short educational videos, each approximately 3 to 5 minutes in duration, these videos were sent individually to each participant every alternate day from Monday to Friday, resulting in three videos per week over a period of one month, Reminders were sent the following day after each video to encourage engagement and

sustain behavior change. Each week was focused on specific HBM constructs delivered through short, professionally scripted educational videos in Urdu.

In Week 1, participants were introduced to the link between diabetes and oral health and the importance of maintaining good oral hygiene. Week 2 focused on perceived susceptibility and severity by highlighting the increased vulnerability of diabetic patients to oral complications and the consequences of poor hygiene practices. Week 3 addressed perceived benefits, perceived barriers, and cues to action by explaining how adopting oral-health behaviors can reduce complications, improve comfort, and minimize treatment costs, while also identifying common challenges and strategies to overcome them. Week 4 strengthened perceived self-efficacy by demonstrating correct oral-care techniques, such as brushing technique, flossing, tongue cleaning, and gum massage, enabling participants to confidently perform these behaviors independently.

All educational materials underwent expert review by dentists, public health specialist and Endocrinologist prior to implementation to ensure clarity, cultural sensitivity, and scientific accuracy. Adherence to the intervention was monitored through WhatsApp by sending follow-up messages and engaging reminders. The control group received only a printed brochure containing basic oral-health information and routine care during the study period. However, after the study concluded, the control group was also provided access to the same educational videos to ensure ethical equity and allow them to benefit from the intervention content.

Figure 3.2: Educational brochure given to the control group, containing oral-health information related to diabetes mellitus.

[figure not shown]

Figure 3.3: Some Screenshots from oral-health educational intervention videos shared via WhatsApp, illustrating a. demonstrations of link between diabetes and oral health, b. proper brushing technique, c. oral complication of diabetes and d. flossing technique.

## **Data Analysis Procedure**

Data were analyzed through a statistical package for Social Sciences (SPSS) version 26. Frequency and percentages were reported for qualitative variables. Mean and standard deviations were reported for normally distributed quantitative variables while median and interquartile ranges were reported for non-normally distributed quantitative variables. Normality of quantitative variables were assessed using Shapiro-wilk's test of normality. The Independent sample t-test was conducted to compare the mean scores of perceived barriers and behavior between the intervention and control groups. For all other constructs, which were not normally distributed, the Mann-Whitney U test was applied. For within-group comparisons of pre and post scores of behaviors and perceived barriers, the Paired sample t-test was used. The Wilcoxon signed rank test, was used for the remaining variables that were not normally distributed. Stratification was carried out based on gender, diabetes duration, and education level to see the effect of these modifiers on outcome (control vs. intervention) using Chi-square test. A p value less than and equal to 0.05 was considered as significant.

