## **Operational Definitions**

### **Oral Hygiene-Related Behaviors:**

Participants' reported frequency and quality of oral health practices, including brushing, flossing, gingival health, and dental visits, measured on a scale of 0(never) to 4(always) using performance related questions. Higher scores will indicate better oral hygiene related behaviors. Pre and post intervention scores were compared, and cutoff levels were determined using the mean and standard deviation (SD).(7)

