### **Sampling Technique and Randomization**

A convenience sampling technique was used to recruit participants from the outpatient diabetes clinic at DUHS. Patients who are present at the clinic for their routine appointments and meet the eligibility criteria was approached. They were informed about the study objectives and procedures, and those who agreed to participate was asked to provide written informed consent. After enrollment, participants were randomly assigned to either the intervention group or the control group, following a 1:1 allocation ratio. The randomization process was stratified based on three key characteristics including gender, educational level, and duration of diabetes, to ensure balanced distribution and to minimize potential bias.

Randomization was conducted using random number generator where each participant was assigned a random number, then participants were allocated equally into either Intervention Group which received HBM based education via WhatsApp or control Group which received an educational brochure. This study was single blinded in which participants were not informed about the presence of two distinct groups; they were only aware about receiving education related to oral health.

[figure not shown]

Figure 3.1. Flow diagram of patient selection and allocation into intervention and control groups

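### Behavior and perceived barriers are compared between arms without adjustment for baseline score or stratification factors; a disclosed ANCOVA would add precision if baseline and follow-up scores correlate at about 0.5 or more

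*Combined protocol and SAP*

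**What the plan says.** Data Analysis Procedure is the whole analysis plan.

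- **Behavior and perceived barriers.** "The Independent sample t-test was conducted to compare the mean scores of perceived barriers and behavior between the intervention and control groups".
- **Other scores.** "For all other constructs, which were not normally distributed, the Mann-Whitney U test was applied". This presumably covers knowledge. Survey Instrument, however, places knowledge in its own section, apart from the Health Belief Model constructs ("Section I comprised of 10 items assessing oral-health knowledge"), so that is an inference.
- **Baseline scores.** Data Collection Procedure has the same questionnaire completed at baseline and at one month. In the analysis, baseline enters explicitly only through within-group paired tests.
- **Stratification factors.** Sampling Technique and Randomization states that "The randomization process was stratified based on three key characteristics including gender, educational level, and duration of diabetes". In the analysis these factors appear only here: "Stratification was carried out based on gender, diabetes duration, and education level to see the effect of these modifiers on outcome", by chi-square test.
- **Which score is compared.** The plan does not say whether the t-test uses one-month scores or changes from baseline. Sample Size is built on post-intervention scores, which points to the former. The operational definition of perceived barriers says only "Pre- and post-scores will be compared", and the definition of behavior is no more specific.

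No ANCOVA, regression or other adjusted between-group model is described anywhere.

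**The concern.** A baseline measurement of the same score is usually the strongest available predictor of the follow-up score. A post-score t-test leaves the variation it explains in the error term. A change-score t-test does use baseline, but forces its coefficient to 1, which is inefficient unless the correlation is high. Neither uses the stratification factors, and a chi-square look at modifiers does not adjust a mean difference.

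Validity is not at stake, because randomisation protects the unadjusted tests. The width of the interval is. Hypothesis names behavior as one of its two outcomes, each arm has 49 patients, and the data needed for a sharper comparison are already in hand.

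There is a secondary point. If allocation was balanced within strata and the factors predict the score, the unadjusted test overstates its standard error and is conservative. Whether that applies is unclear: the text claims stratification, but the mechanism described is only that "each participant was assigned a random number, then participants were allocated equally".

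**Working it through.** **Inputs from the documents.** Sample Size: means 4.09 and 3.64 (difference 0.45), SDs 0.49 and 1.01, 49 per arm. Data Analysis Procedure: significance level 0.05, taken as two-sided.

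**Assumptions.** The documents give no SD for behavior or barriers, so these perceived-susceptibility values stand in. The baseline-to-follow-up correlation ρ is not given; 0.3, 0.5 and 0.7 are used. Baseline SD is taken as 0.75, equal in both arms, for the change-score comparison.

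**1. The plan's own figure.** n per arm = (z₁₋α/₂ + z₁₋β)² × (0.49² + 1.01²) / 0.45².

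- Two-sided 0.05 and 80% power: (1.960 + 0.842)² × 1.2602 / 0.2025 = 48.9, so 49.
- The stated 0.01 and 95% power: (2.576 + 1.645)² × 1.2602 / 0.2025 = 110.9, so 111.

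The stated 49 therefore matches 0.05 and 80%. That mismatch is a separate matter, and this point does not depend on it. At 49 per arm, SE = √(1.2602/49) = 0.1604 and z = 0.45/0.1604 = 2.806. Unadjusted power at 0.05 is Φ(2.806 − 1.960) = 0.80.

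**2. Large-sample formulas (equal SDs, baseline only).** The variance of the ANCOVA estimate is 1 − ρ² times that of the post-score difference, and (1 + ρ)/2 times that of the change-score difference. Against post scores the variance factor is 0.91, 0.75 and 0.51 at the three correlations. The interval is √0.91 = 0.954, √0.75 = 0.866 and √0.51 = 0.714 times as wide. The factor against change scores is 0.65, 0.75 and 0.85.

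**3. Simulation at the trial's size.** There were 8,000 trials per setting, with normal scores and the same ρ in both arms. ANCOVA used HC3 errors, baseline and three binary covariates unrelated to outcome; the comparator was a Welch t-test on post scores.

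| Quantity | ρ = 0.3 | ρ = 0.5 | ρ = 0.7 |
|---|---|---|---|
| CI width, ANCOVA / post score | 1.006 | 0.926 | 0.791 |
| Equivalent change in patients, 1/ratio² − 1 | −1% | +17% | +60% |
| Power, ANCOVA | 0.784 | 0.858 | 0.944 |
| Power, post-score t-test | 0.782 | 0.795 | 0.795 |
| Power, change-score t-test | 0.655 | 0.799 | 0.935 |
| CI width, ANCOVA / change score | 0.868 | 0.928 | 0.987 |
| CI width, ANCOVA / post score, equal SDs 0.794 | 1.007 | 0.913 | 0.754 |
| CI width, ANCOVA / post score, six covariate columns | 1.041 | 0.957 | 0.818 |

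Under no effect, ANCOVA with HC3 rejected in 4.3% to 4.6% of trials, so the gain is not bought with false positives. In patients, the equal-SD row is worth −1%, +20% and +76%, and the six-column row −8%, +9% and +50%. With six columns at ρ = 0.7, the ANCOVA interval is 0.818/0.801 = 1.02 times that of the change score.

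**4. Why the formula and the simulation differ.** At ρ = 0.5 the formula gives 13% narrower and the simulation 7%. The simulation carries HC3 errors, unequal SDs and three useless covariates. With baseline only and HC3 errors the simulated ratio is 0.974 at 0.3 and 0.896 at 0.5.

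**5. Break-even against post scores.** This depends on the model. The degrees-of-freedom formula gives √(1 − 94/95) = 0.10 for baseline only and √(1 − 90/95) = 0.23 with four further terms. The three-covariate HC3 simulation gives about 0.32 (ratio 1.006 at 0.30, 0.990 at 0.35).

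**The case against.** The strongest reply is that no error has been shown. The t-tests are valid, they suit the two scores treated as normal, and the trial was sized on a t-test. The gain rests on a correlation the documents do not give and on whether post or change scores were compared. There is nothing to gain at 0.3 over post scores, or at 0.7 over change scores. The power figures borrow the effect and SDs of perceived susceptibility, a construct that the plan sends to the Mann-Whitney test. The stratification covariates were simulated as unrelated to outcome, so in these numbers they only cost precision. Only one of the two scores is in the hypothesis. Finally, Study Duration shows that the study has ended, so the analysis would be post hoc in a plan that names no primary outcome.

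Most of this stands as a limit on the claim. The gain is conditional, the power figures illustrate rather than predict, and the new analysis cannot displace the planned one. It does not remove the point. The equal-SD width ratios do not depend on the scale of the score. Useless covariates make the estimate of gain cautious, and baseline alone already helps slightly at 0.3. The unknown correlation also argues for ANCOVA: it stays near the better of the two unadjusted tests across the range and beats both at 0.5, whereas choosing post or change scores in advance risks the worse one.

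**Conclusion.** The concern holds as a matter of precision for behavior and perceived barriers only. Against a post-score t-test, a baseline- and strata-adjusted ANCOVA gives about the same interval at a correlation of 0.3, 4% to 9% narrower at 0.5 and 18% to 25% narrower at 0.7, across the SD and covariate settings tried. Against change scores, with three covariates, the interval is 13%, 7% and 1% narrower. The worst cases are 4% wider than post scores and 2% wider than change scores, both with six covariate columns.

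A correlation of about 0.5 is enough for a material gain; it is not a threshold below which adjustment fails. The sizes rest on assumed correlations, on SDs borrowed from another score, on normal data and on 49 analysed patients per arm. No gain is claimed for the Mann-Whitney scores. The change should be made, but the planned results remain valid without it.

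**What to change.** For behavior and for perceived barriers, add an ANCOVA of the one-month score on group, the baseline value of that score, gender, education level and diabetes duration, with HC3 standard errors. Report the adjusted difference with its 95% interval. Label it post hoc, show the planned t-test beside it, and do not choose between them on the result. Code education and duration in few levels and state the coding.

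For the skewed scores keep Mann-Whitney as the test. An ANCOVA there is an optional sensitivity analysis and should not be presented as more powerful.

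Also state whether post or change scores were compared and which test was used for knowledge. Base the conclusion on the hypothesis on the between-group comparison, with within-group changes as description.

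The cost is one extra analysis for each of two scores and no new data. It uses one degree of freedom for baseline and three for the factors if each has two levels. The documents give no levels, and more of them shrink the gain.

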## Sample Size

Sample size was calculated using OpenEpi online software, based on two independent sample t-test by using mean and standard deviation of post intervention perceived susceptibility score

which were  $4.09 \pm 0.49$  in intervention group and  $3.64 \pm 1.01$  in control group in the study conducted by Malekmahmoodi et al. (2020)(7). A sample size of 49 achieved in each group, power 95% with a significance level (alpha) of 0.01. Total 98 patients have been recruited and divided into 49 patients in each group (two groups).

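### Perceived susceptibility is sized on a t-test of means but analysed by Mann-Whitney, and the rank-tested scores have no between-arm estimate or confidence interval

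*Combined protocol and SAP*

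**What the plan says.** The Sample Size section states that the calculation was "based on two independent sample t-test by using mean and standard deviation of post intervention perceived susceptibility score". It takes 4.09 (SD 0.49) and 3.64 (SD 1.01) from an earlier trial and concludes: "A sample size of 49 achieved in each group, power 95% with a significance level (alpha) of 0.01".

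The Data Analysis Procedure states: "Normality of quantitative variables were assessed using Shapiro-wilk's test of normality". The independent-samples t-test is then assigned to perceived barriers and behavior. For the rest: "For all other constructs, which were not normally distributed, the Mann-Whitney U test was applied". Perceived susceptibility falls in this second group. So, on a natural reading, does knowledge, since no other between-arm test is given for it. The summary named for such scores is that "median and interquartile ranges were reported for non-normally distributed quantitative variables". Significance is judged at 0.05.

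Under Scoring, each Health Belief Model construct is reported on a 1-to-5 range. Under Survey Instrument, susceptibility has seven items. The stated objective is to compare the effectiveness of WhatsApp education and brochures.

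**The concern.** The one score on which the trial was sized is not analysed by the test it was sized for. The t-test calculation concerns a difference in means. Mann-Whitney concerns whether a randomly chosen patient in one arm tends to score higher than one in the other. The two agree when the distributions differ only by a shift. The plan's own SDs, 0.49 and 1.01, make a pure shift implausible on a scale bounded at 1 and 5.

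Two things are at stake. First, the power quoted for susceptibility does not belong to the test that is used. Second, a comparison of effectiveness needs an estimated difference and its precision. For the rank-tested scores a reader gets two medians and a p-value. Which scores are compared by means and which by ranks was settled by a normality test on the data, so results on the same 1-to-5 scale cannot be set side by side.

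**Working it through.** **Inputs.** From Sample Size: means 4.09 and 3.64, SDs 0.49 and 1.01, 49 per arm. From Scoring: range 1 to 5. From Data Analysis Procedure: alpha 0.05. Sidedness is not stated; two-sided is assumed. Score shapes are assumptions throughout.

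**Step 1: what 49 per arm buys with a t-test.** n per arm = (z for alpha + z for power)² × (0.49² + 1.01²) / 0.45².

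- The variance term is (0.2401 + 1.0201) / 0.2025 = 6.223.
- Two-sided 0.05 and 80% power: (1.960 + 0.842)² × 6.223 = 48.8, so 49.
- Two-sided 0.01 and 95% power, as stated: (2.576 + 1.645)² × 6.223 = 110.9, so 111.

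The stated 95% and 0.01 are not reproduced. That is a separate matter. Here it means only that any power comparison must start from about 80% at 0.05.

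**Step 2: what Mann-Whitney responds to.** Its power is driven by P, the probability that an intervention score exceeds a control score. For normal scores P = Φ(0.45 / √1.2602) = Φ(0.401) = 0.656. Means and SDs alone do not fix P. With the same means and SDs it is 0.604 for normals truncated to 1-5, and 0.694 for a Laplace shape (which runs past the scale).

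**Step 3: simulated power**, 49 per arm, two-sided 0.05, 4,000 to 20,000 trials per scenario. Small differences between runs are simulation error.

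| Assumed shape | Welch | Mann-Whitney |
|---|---|---|
| Normal, plan's SDs | 79% | 76-77% |
| Normal, equal SDs of 0.794 | 79% | 77% |
| Beta on 1-5, plan's SDs | 80-81% | 42-44% |
| Truncated normal on 1-5 | 80-81% | 44% |
| Maximum-entropy, 7-item grid | 81% | 46% |
| 7-item latent model | 80-81% | 50-53% |
| Control bimodal within 1-5 (SD 0.92) | 84% | 58% |
| Control near 3 plus ceiling cluster (SD 0.98) | 81-84% | 60% |
| Control tight centre plus two tails (three versions) | 81-84% | 68%, 72%, 80% |
| Control central spike, tails at 1 and 5 | 82% | 87% |
| Beta on 1-5, equal SDs of 0.79 | 78-80% | 86-87% |

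The low beta figure has a visible cause. For the control arm the scaled mean is (3.64 − 1)/4 = 0.66 and the scaled variance is (1.01/4)² = 0.0638. Then 0.66 × 0.34 / 0.0638 − 1 = 2.52, and the beta parameters are 0.66 × 2.52 = 1.66 and 0.34 × 2.52 = 0.86. The second is below 1, so the assumed control density rises all the way to 5. Many control patients then outrank intervention patients despite the lower control mean.

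Shapes that run past 1-5 go both ways. Laplace gives Mann-Whitney 92% against 79-80%, and right-skewed gamma 83-98% against 77-79%. Left-skewed gamma gives 57-70% against 80-84%.

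**Step 4: equal means, SDs 0.49 and 1.01.** Mann-Whitney rejects at 0.05 in about 6% of trials for normal scores, 13-14% for beta scores at mean 3.64 and 33-34% at mean 4.0. Welch rejects in about 5%. In the two beta cases P is 0.455 and 0.412, so the rejections lean toward the wider-spread control arm.

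**Step 5: the normality screen.** A symmetric 0-10 integer score (binomial, p = 0.5) fails Shapiro-Wilk in 74% of samples of 49 and in all samples of 98, while the t-test on it holds 5%. Failing the screen is therefore weak evidence against a t-test at this sample size.

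**The case against.** Mann-Whitney with median and interquartile range is a conventional and internally coherent choice for non-normal Likert scores. Preferring Welch for every score is partly a preference, and a sensitive normality test does not make the rank test invalid. That stands.

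A reader might infer that the plan's unequal SDs by themselves cut power, or that the trial has lost nearly half of it. The documents do not support this. Under normality the loss is about 3 points, and only about 1 of these comes from the unequal SDs (equal SDs already cost about 2). The large losses come from assumed shapes. Other shapes within 1-5 give 58-80%, and a central spike with tails favours Mann-Whitney. The SD ratio comes from one outside trial and applies to susceptibility alone, so nothing can be said about power for the other scores. The plan does say that susceptibility was not normal, so the normal case cannot be relied on for reassurance either.

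A reader might also take Step 4 as inflated type I error. It is not: Mann-Whitney holds 5% when the two distributions are identical. The scenario requires an intervention that changes spread but not mean, which no document proposes, and in the beta runs the error would favour control.

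Finally, the Hypothesis concerns knowledge and behaviors. Behavior keeps its t-test, and susceptibility is nowhere named as the primary outcome. This limits the consequence of the sizing mismatch. It does not touch the missing estimate, which on the natural reading affects knowledge too.

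**Conclusion.** Two points hold on the text alone. The sizing of perceived susceptibility describes a t-test of means that the plan does not run on that score. And the rank-tested scores have no named between-arm difference or confidence interval, so they cannot answer a question about comparative effectiveness beyond a p-value.

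A third point holds given the plan's SDs: Mann-Whitney does not track mean scores here, and its result can mislead about them.

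The power consequence is conditional. At 49 per arm and two-sided 0.05, Welch has about 79-84%. Mann-Whitney has about 76-77% if normal and roughly 42-87% over the bounded shapes tried; with equal SDs it can be the more powerful test. These figures rest on the outside trial's means and SDs, no dropout and assumed shapes. This should be fixed; it is not grounds for setting the trial's results aside.

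**What to change.** In the Data Analysis Procedure, for every score (knowledge, each Health Belief Model construct, behavior), report the between-arm difference in means with its 95% confidence interval from the unequal-variance (Welch) t-test, and do not select the test by Shapiro-Wilk. Keep Mann-Whitney, with the probability of superiority, as a labelled sensitivity analysis. Since the data are already collected, date the change, label it as such and show both results for every score.

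If Mann-Whitney stays the main test for susceptibility, the Sample Size section should say that the t-test calculation does not give the power of that test and that its power depends on the assumed score shape. No single replacement figure should be inserted, because the documents cannot support one.

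The cost is wording and a re-run in SPSS, with no new patients or measurements. The one drawback is that scores near the ceiling are summarised by means, which the rank-based sensitivity analysis covers.
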